9 CRITERIA FOR DISCONTINUATION

9.1 Permanent and Premature Treatment Discontinuation

- Drug-related toxicity or allergic reaction (see [section 8.0](#)).
- Requirement for prohibited concomitant medications (see [section 5.4.1](#)).
- Request by participant to terminate treatment.
NOTE: The reason for treatment discontinuation should be documented (e.g. concern for AE, lack of efficacy, or other reason).
- Clinical reasons believed life threatening by the physician, even if not addressed in the [section 8.0](#) of the protocol.

9.2 *Premature Study Discontinuation*

- 9.2.1 Failure to take the first dose (directly observed/confirmed over telephone) of study treatment within 2 days of study entry.
- 9.2.2 Request by the participant to withdraw consent.
- 9.2.3 Request of the health care provider if she or he thinks the study is no longer in the best interest of the participant.
- 9.2.4 At the discretion of the IRB/EC, FDA, NIAID, Office for Human Research Protections (OHRP), other government agencies as part of their duties, investigator, or industry supporter.

In the event that a participant prematurely discontinues from the study, unless they have withdrawn consent, sites will attempt to obtain information regarding vital status (including date last seen alive, hospitalization, date of death, and primary cause of death) from other sources (such as family members, other designated contacts, or clinic records) per [section 6.2.15](#).

10 STATISTICAL CONSIDERATIONS

10.1 *General Design Issues*

This is a double-blind placebo-controlled pilot trial to document safety and efficacy endpoint assessments and to determine the feasibility of community recruitment and enrollment of symptomatic adult outpatients with COVID-19.

The observational data from Wuhan comparing hospitals with and without the use of this TCM demonstrated a reduction of 10% progression without this TCM to 2-5% with this TCM. A key difference in patient care in the US is that patients with mild and moderate symptoms are staying home having been asked to self-quarantine. Initial data on hospitalization rates in the US in early 2020 points to rates of above 20%.

A reasonable target of reduction through the use of the Xuanfei Baidu Granules would likely reduce the progression rate among those with mild/moderate symptoms, from 20% to 10%, which has the potential of an almost 30% reduction of fatalities, depending on the distribution of severity of disease at diagnosis in the population.

10.2 *Outcome Measures*

Primary and secondary outcome measures listed below will be utilized in the future studies' primary Statistical Analysis Plan, which will define the content of the Primary Analysis Report.

10.2.1 Primary Outcome Measure

- 10.2.1.1 To document the feasibility of recruitment in the community setting by assessment of the number of positive cases identified per week.
- 10.2.1.2 To document the proportion of patients who agree to participate as measured by enrollment and randomization.
- 10.2.1.3 To document the treatment emergent side effects and safety profile of the XFBD and placebo.
- 10.2.1.4 To document the rate of hospitalization or death within 42 days of enrollment in the XFBD and placebo treated groups.

10.2.2 Secondary Outcome Measures

- 10.2.2.1 To document the effect of XFBD on Symptom Severity Score within 28 days of

study entry.

- 10.2.2.2 To document the proportion of patients who are compliant taking greater than 90% of the test substance as measured by self-report
- 10.2.2.3 To document the proportion of patients who comply with symptom monitoring.
- 10.2.2.4 To document the proportion of patients who comply with repeated clinical testing.
- 10.2.2.5 To document cumulative incidence of serious adverse events, and adverse events leading to early discontinuation of XFBD or placebo.
- 10.2.2.6 To document cumulative incidence of grade 3 and 4 adverse events.
- 10.2.2.7 To obtain levels (detectable versus not detectable, and continuous on log10 scale) of SARS-CoV-2 RNA from nasal swabs at approximately days 1, 7 and 14 among a subset.

10.3 *Randomization and Stratification*

[figure not shown]
Eligible participants will be randomized using a 1:1 ratio to each of the study arms. Housemates of participants previously enrolled will be independently randomized so that housemates will not be clustered within treatment group.

Randomization will be stratified by “high” vs “low” risk of severe disease, where “high” risk is defined by any of the following: age ≥ 60 years, or having any of a number of conditions, as described in section 3.3.

10.4 Sample Size and Accrual

Pilot studies have many important purposes, as described in the objectives for this study (sections 1.1, 1.2, and 1.3). However, the use of pilot studies to determine effect sizes for future larger studies is not recommended since such estimates tend to be both biased and very unstable due to the small pilot study size.(75) We illustrate this graphically for this study in Figure 1. Our current estimate is that the event rates in the control and XFBD groups will be 0.20 and 0.10, respectively. Thus, the relative risk estimate is 0.50. If these estimates are in fact attained in the pilot study, it will support our assumption, yet only mildly, since the 80% confidence interval for that relative risk (given the 20% event rate in the control group) will be 0.26-0.97. Furthermore, the environment in which COVID-19 statistics are emerging is rapidly evolving due to changes in such factors as testing rates and exposure rates within subpopulations. At the time when we are putting forward a new trial proposal, we will look at the most recent data in order to make the best possible estimate for the treatment effect.

[figure not shown]
Figure 1

In addition to the relative risk, the event rate in the control group will be estimated in order to establish an appropriate sample size for a future study. Again, we will look at the most recent data available at the time of the study proposal to inform our hypothesis. The control group event rate, however, is expected to vary by the type of population sampled, so data specific to our sampling methods will be useful. As shown in Figure 2, the confidence intervals aren't narrow, yet they provide guidelines for sensitivity analyses in estimating future necessary sample sizes.

Figure 2

80% Confidence Interval by Event Rates for Control Group (N=30)

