Once infection occurs, the clinical course is variable. Best current data suggests that fewer than 2.5% of infected persons will show symptoms within 2.2 days (CI, 1.8 to 2.9 days) of exposure, and symptom onset will occur within 11.5 days (CI, 8.2 to 15.6 days) for 97.5% of infected persons" (3) In most (~80%) cases, COVID-19 presents as a mild-to-moderately severe, self-limited acute respiratory illness with fever, cough, and shortness of breath. It remains unclear exactly what the rate of progression of COVID-19 is and what the predictors are for complications, including pneumonia, acute respiratory distress syndrome (ARDS), kidney failure, and death. It is also clear that older age, male sex, and comorbidities, including diabetes and hypertension, increase the risk for worse outcomes (Figure 2.1-1) (4-6). In a recent meta-analysis, the main clinical symptoms were fever (88.5%), cough (68.6%), myalgia or fatigue (35.8%), expectoration (28.2%), and dyspnea (21.9%). Minor symptoms included headache or dizziness (12.1%), diarrhea (4.8%), and nausea and vomiting (3.9%). Laboratory examinations showed that lymphocytopenia (64.5%), increase of C-reactive protein (CRP) (44.3%), increase of lactate dehydrogenase (LDH) (28.3%), and leukocytopenia (29.4%) were more common in those with COVID-19 (7).

[figure not shown]

Figure 2.1: Timeline of COVID Disease Progression after Hospitalization.

Onset refers to onset of symptoms.

Viral infections jump from host to host through a variety of pathways. CoVs do this through respiratory droplets. Understanding this shedding is important to understanding epidemic spread and how shedding relates to disease progression. The best evidence available now suggests that viral shedding, especially in upper respiratory secretions, is detectable around 2 days before symptoms develop in people and continues throughout the symptomatic phase. This shedding can be quite high during active disease and can continue for up to 37 days, with a quarter of persons still shedding at 3 weeks, as detected by nasopharyngeal swabs (4).

Biomedical Interventions

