Wuhan Experience: Wuhan Jiangxia *Fangcang* Hospital used TCM prescriptions and other traditional methods (such as acupuncture, guasha, medicinal patches, etc.) in the treatment of COVID-19 while continuing the patient's previous conventional medicines for underlying health conditions. From February 14th to March 10th, the hospital treated a total of 564 patients with mild (71%) and moderate (29%) COVID-19. Upon hospitalization, approximately 30% of the patients had symptoms of fatigue and shortness of breath, while another approximately 40% had cough. Within the 14-day treatment and subsequent observation period, 482 patients recovered and were discharged. Among the patients admitted, none of their conditions progressed to severe or critical. It is of note that at Wuhan Jiangxia *Fangcang* Hospital, two main prescriptions with the addition of other TCM treatment modalities were used. The medical staff was also free of infection [personal correspondence with [name] [name] dated March 31, 2020]

For the *Xuanfei Baidu* prescription, which was given to 273 patients, none of them progressed to severe or critical condition. 250 patients achieved two consecutive negative viral RNA tests in which the average time frame was about 11.02 ± 3.59 days, with a 95% confidence interval (CI). 230 patients saw a significant improvement in their CT scans in about 13.13 ± 4.20 days with a CI 95%. [personal correspondence with [name], dated April 28, 2020]

At another *fangcang* hospital which had 330 patients, TCM was not used or if used, in an unstandardized manner, and 32 patients (9.7%) of those patients progressed to severe or critical condition. Other *fangcang* hospitals that utilized TCM prescriptions also saw a decrease in patients' progression of disease to approximately 2-5%. [personal correspondence with [name] [name] dated March 31, 2020]

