The elderly above the age of 75 are excluded in consideration of the higher possibility of multiple underlying conditions that may or may not be controlled at the time of infection. While the trials done in Wuhan saw no interaction with maintenance medications, the presence of multiple medications may have increased risk and complications that are not yet studied. Future trials will address this cohort of patients.

Justification for Comorbidity Restrictions

Individuals with multiple comorbidities have greater risks present, and there is no available data for patients with multiple comorbidities. Individuals with uncontrolled underlying conditions also present with more risk and complications. Without safety data available for these populations, these patients are to be excluded.

Justification for Vaccinated Individuals

The phase 3 clinical trial data for both available messenger RNA (mRNA) vaccines showed efficacy in preventing severe symptomatic COVID-19 disease. The mRNA-1273 (Moderna) vaccine showed 94.1% efficacy at 14 days after the second dose (64) while the BNT162b2 (Pfizer) vaccine showed 95% efficacy at 7 days after the second dose. (65) Out of 36,659 California healthcare workers, 379 persons tested positive for SARS-CoV-2 at least 1 day after vaccination, and 270 (71%) of those persons tested positive within the first 2 weeks of receiving the first dose. (66). There was no regular testing after the vaccination, therefore, it is safe to assume those who were reinfected experienced certain symptoms. In Los Angeles, about 62% have gotten their first dose and 53% have received both. (67) With any level of probability for symptomatic reinfection, the vaccinated population are still eligible for XFBD.

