3. STUDY DESIGN

The pilot phase is a double-blind, placebo-controlled randomized component designed to document safety and efficacy endpoint assessments and to determine the feasibility of recruitment and enrollment of symptomatic, community dwelling, adult, outpatients with COVID-19 as well as patient compliance with the protocol.

The pilot phase will enroll a total of 60 participants (30 in each arm). Participants will be followed for 14 days on treatment with an additional 10 weeks off treatment. Participants who do not start study treatment will be replaced. Participants will be randomized 1:1 as individuals. Participants will receive either XFBD (10 g orally twice a day) for 14 days or a placebo twice a day for 14 days.

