4.3.7 Known allergy/sensitivity or any hypersensitivity to components of XFBD

4.3.8 Active drug or alcohol use or dependence that, in the opinion of the site investigator, would interfere with adherence to study requirements.

4.3.9 Has known prior kidney disease.

4.3.10 Has known cirrhosis, acute liver disease or uncontrolled chronic liver disease.

4.3.11 Has known severe coronary artery disease.

4.3.12 Has known narrow angle glaucoma.

4.3.13 Has greater than two or a single uncontrolled underlying comorbid condition including cardiovascular disease (coronary artery disease, heart failure, valvular heart disease), hypertension, diabetes, chronic lung disease, chronic kidney disease, chronic liver disease, immunocompromised (HIV or daily users of more than 5 mg/day of prednisone), prior organ transplant.

4.3.14 Fulfils the FDA EUA criteria of at high risk for progressing to severe COVID-19. This includes high-risk individuals specified in the EUA who meet at least one of the following criteria: Body mass index (BMI) \geq 35; Chronic kidney disease; Diabetes mellitus; Immunocompromising condition/immunosuppressive disease; Currently receiving immunosuppressive treatment; Aged \geq 65 years; or Aged \geq 55 years and have: Cardiovascular disease, or Hypertension, or Chronic obstructive pulmonary disease/other chronic respiratory disease. If the patient is not able to receive the EUA agent because of unavailability this exclusion may be waived.

4.3.15 Women who are currently pregnant or breastfeeding.

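### The 0.20 control event rate in 10.4 has no source for the population this trial enrols, and the plan does not record all that is needed to interpret the rate the pilot will observe

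*Combined protocol and SAP*

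**What the plan says.** Section 10.4 gives the planning rates: "Our current estimate is that the event rates in the control and XFBD groups will be 0.20 and 0.10, respectively". It then illustrates precision at those rates: "80% confidence interval for that relative risk (given the 20% event rate in the control group) will be 0.26-0.97". It adds that the pilot's control rate will be estimated to help size a future study.

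Section 10.4 names no source for 0.20. The nearest support is in 10.1: "Initial data on hospitalization rates in the US in early 2020 points to rates of above 20" per cent. That sentence states no restriction by severity, age or comorbidity. The next paragraph of 10.1 applies a fall from 20% to 10% to people with mild or moderate symptoms.

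The eligibility rules describe a narrower group. Section 4.2 limits entry to mild or moderate disease and ages 18 to 75. Section 4.3 excludes need for hospitalisation, severe or critical disease, and more than two comorbidities or a single uncontrolled one. Section 4.3.14 excludes people who meet the EUA high-risk criteria, but "If the patient is not able to receive the EUA agent because of unavailability this exclusion may be waived". Section 2.2 (Justification for Vaccinated Individuals) concludes that "the vaccinated population are still eligible for XFBD".

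Section 2.2 (Wuhan Experience) gives a figure for a hospital with 330 patients where TCM was unused or unstandardised: "32 patients (9.7%) of those patients progressed to severe or critical condition". The Summary in 2.2 and section 10.1 both put progression without TCM at about 10%; the Summary refers this to mild and moderate cases.

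**The concern.** A rate from the first months of the US epidemic, with no stated limit on severity, is carried into a June 2021 protocol whose entry rules remove many higher-risk patients and admit vaccinated people. Nothing in 10.1 or 10.4 adjusts for this.

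Two things depend on it. The relative-risk interval in 10.4 is explicitly conditional on a 20% control rate, so a lower rate would make the pilot less informative than the illustration suggests. And the observed control rate is to be carried into the next trial's sample size. That needs a description of who the controls were. Two features that may shift their risk, vaccination and entry under the 4.3.14 waiver, are not among the reporting factors in 10.6.

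**Working it through.** **1. The plan's own interval.** Inputs from 10.4 and section 3: rates 0.20 and 0.10, 30 per arm. The standard error of the log relative risk is sqrt(0.90/(30 × 0.10) + 0.80/(30 × 0.20)) = sqrt(0.300 + 0.133) = 0.658. The two-sided 80% interval is 0.50 × exp(±1.2816 × 0.658) = 0.22 to 1.16. The printed 0.26 to 0.97 is not reproduced. A multiplier of 1.00 gives 0.50 × exp(±0.658) = 0.26 to 0.97, which is a 68% interval. Holding the control rate fixed at 0.20, an 80% log interval is 0.25 to 1.01 and a Wilson interval 0.25 to 0.96, so neither matches. This is a separate error in the same paragraph. The table below uses the multiplier 1.2816.

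**2. Candidate sources for the control rate.**
- 10.1: US, early 2020, above 20%. The endpoint is hospitalisation and no severity limit is stated.
- 2.2: China, 32/330 = 9.7%, and about 10% nationally. The endpoint is progression to severe or critical disease.
- Needed: hospitalisation or death within 42 days, in mild or moderate US outpatients who pass 4.3, some of them vaccinated.

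Neither source matches on both endpoint and population.

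**3. Risk strata (3.3) against the waiver group (4.3.14).** Each case assumes no other risk factor.
- BMI 35 to 40: low risk in 3.3, but enters only by waiver.
- Age 55 to 59 with hypertension on one drug: low risk in 3.3, but enters only by waiver.
- Diabetes, or age 65 and over: high risk in 3.3, and enters only by waiver.
- Age 60 to 64 without comorbidity: high risk in 3.3, and no waiver needed.

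Both strata can therefore hold waived and non-waived patients, in proportions that depend on EUA supply. Vaccination is in neither definition. The medical history in 6.2.19 specifies signs, symptoms and diagnoses of the past 14 days, and 6.2.20 covers medication over three months, so an earlier vaccine dose can be missed.

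**4. What a lower rate would do.** The relative risk is held at 0.50 with 30 per arm. Expected events are 30 × rate, and the chance of no control event is (1 − rate)^30. The last column is the size of a future trial at two-sided 5% and 80% power. Those are conventional values assumed here, as the plan states none. The formula is n = [1.96·sqrt(2p̄(1−p̄)) + 0.8416·sqrt(p1(1−p1) + p2(1−p2))]² / (p1−p2)². At 0.20 v 0.10 this is (1.96 × 0.505 + 0.8416 × 0.500)² / 0.01 = 199.

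| Control rate | Basis | Expected events, control v XFBD | No control event | 80% interval for RR | Next trial, per arm |
|---|---|---|---|---|---|
| 0.20 | 10.4 | 6 v 3 | 0.1% | 0.22–1.16 | 199 |
| 0.10 | 2.2 and 10.1, different endpoint | 3 v 1.5 | 4% | 0.14–1.72 | 435 |
| 0.05 | assumption | 1.5 v 0.75 | 21% | 0.08–2.97 | 906 |

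A trial sized on 0.20 v 0.10 (199 per arm) would have 47% power if the true rates were 0.10 v 0.05, and 26% if they were 0.05 v 0.025.

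**The case against.** The case against is substantial, and much of it stands.

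- **The rate sizes nothing here.** The 60 participants are not derived from 0.20, and 10.6 says the pilot is not powered for treatment differences. This stands. A reader might infer that the plan promises event counts it cannot deliver, but it states none.
- **10.4 already hedges.** It warns that pilot effect sizes are unstable, expects the control rate to vary with the population, and commits to recent data when the next trial is proposed. The title of Figure 2 suggests a range of control rates is shown. This stands as far as it goes. It does not source the 0.20 or change a relative-risk interval conditional on it, and later external data cannot supply participant characteristics that were not recorded.
- **The 10% is another endpoint in another setting.** This stands. It would be tempting to call 10% the protocol's own upper limit, but progression to severe disease in China does not bound hospitalisation or death in US outpatients. Likewise "In most (~80%) cases, COVID-19 presents as a mild-to-moderately severe, self-limited acute respiratory illness" describes presentation, not the risk of later admission.
- **Vaccine efficacy does not give the rate.** This stands. The 94 to 95% figures in 2.2 concern prevention in vaccinated people generally. They do not give the risk of admission once a vaccinated person has symptomatic infection.
- **The mix is already described.** Risk group is a randomisation stratum, 10.6 reports by age and risk group, and 10.6.1 allows covariate adjustment. A reader might infer that the control rate will be uninterpretable, or that supply alone will swing it severalfold. The first ignores these provisions. The second needs subgroup rates and waiver shares that the documents do not give. What remains is the mismatch in step 3.
- **Waiver status could be derived.** Anyone enrolled who meets the EUA criteria entered by waiver, and those criteria must be checked at screening. This stands if the answers are kept as data. The screening form and eCRFs are not in the supplied text, so nothing here shows that vaccination or waiver status goes uncollected, only that the protocol text does not name them.
- **Cells will be tiny.** This stands, so the breakdown can only be descriptive.

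**Conclusion.** The 0.20 (and with it the 0.10) has no source for the enrolled population. That it comes from the early-2020 figure in 10.1 is a fair inference, since 10.4 cites nothing. The entry rules make a lower rate likely, but the documents do not settle how much lower.

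The pilot's size and randomisation are unaffected. The effect is on information and on later use. Expected control events fall from 6 to 3 at 10% and to 1.5 at an assumed 5%, and the 80% relative-risk interval widens from 0.22–1.16 to 0.14–1.72 and 0.08–2.97. These figures assume a relative risk of 0.50 throughout.

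Reporting by age and risk group describes the control mix only in part, because the strata and the waiver group cut across each other and neither uses vaccination status. This should be corrected because the correction is cheap and the control rate is meant for onward use. It is not a flaw that invalidates the pilot.

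**What to change.** In 10.1 and 10.4, present 0.20 as an unverified value within a range that also includes about 10% (labelled as progression to severe disease in China) and lower values labelled as assumptions. Give expected events and the relative-risk interval across that range, as in the table above, and correct or relabel the printed 80% interval at the same time.

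Add two screening fields: vaccination status with date of last dose, and whether the participant was enrolled under the 4.3.14 waiver. Add both to the descriptive factors in 10.6 for 42-day hospitalisation or death. State there that cells will be small and that the pooled control rate should not be carried to a trial with a different mix.

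The cost is two screening fields, one more descriptive table and a less favourable stated rate. No extra participants are needed, and eligibility and treatment do not change.

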10.6 Analyses

All descriptive statistics will be documented in total and stratified by age, race/ethnicity, gender, risk group and assigned treatment, when applicable. This pilot study is not powered to find statistically significant differences by treatment group.

All analyses involving randomized comparisons will include all randomized participants who received the first (**confirmed**) dose of study treatment, according to a modified intention-to-treat approach. However, as the study is blinded, the use of a modified intention-to-treat approach should not introduce bias into the comparison of randomized arms in this pilot study or in future larger-scale studies.

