10.6.1 Primary Outcome Measure

The first two primary outcomes involve participant enrollment, and these results will help us to plan recruitment for a subsequent larger clinical trial. For example, these results may indicate that special efforts may be needed in the future to recruit certain underrepresented populations. The second two primary outcomes involve health events that will be analyzed with logistic or negative binomial regression models stratified and/or adjusted for covariates, for future planning purposes only.

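### Section 10.4 labels 0.26-0.97 an 80% confidence interval for a relative risk of 0.50, but with 30 per arm the 80% interval is about 0.22-1.16; the printed limits match plus or minus one standard error, about 68%

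*Combined protocol and SAP*

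**What the plan says.** Section 10.4 warns against taking effect sizes from pilot studies and then illustrates the instability for this trial. The inputs are stated: "Our current estimate is that the event rates in the control and XFBD groups will be 0.20 and 0.10, respectively". It continues, "Thus, the relative risk estimate is 0.50". If those values are observed, the plan regards the support for its assumption as slight, "since the 80% confidence interval for that relative risk (given the 20% event rate in the control group) will be 0.26-0.97".

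The sample size comes from section 3: "The pilot phase will enroll a total of 60 participants (30 in each arm"). Section 3 adds, "Participants who do not start study treatment will be replaced", so 30 per arm is also the planned number analysed. Section 10.4 uses the same number in the title of Figure 2: "80% Confidence Interval by Event Rates for Control Group (N=30").

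The readable text of section 10.4 gives no formula or method name for the interval. The graphics of Figures 1 and 2 could not be seen for this review.

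**The concern.** Three and six events are few for an interval that lies wholly below 1, even at the 80% level. The stated rates, sample size and confidence level are enough to recompute the interval, and the result does not agree with the printed limits.

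The sentence is there to show how imprecise a pilot relative risk would be. If the limits are too narrow for their label, they understate that imprecision. They also place an interval that excludes 1 beside the remark about slight support, when the two-sample 80% interval includes 1. Section 10.4 intends the control-rate intervals in Figure 2 to guide sensitivity analyses for the size of a later trial. The same slip there, if it was made, would carry into that use.

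**Working it through.** **Inputs.** Control rate 0.20, XFBD rate 0.10, relative risk (RR) 0.50, level 80% (section 10.4); 30 per arm (section 3). Expected events: 6/30 on control and 3/30 on XFBD.

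**Standard error.** SE(log RR) = sqrt(1/3 - 1/30 + 1/6 - 1/30) = sqrt(0.9/3 + 0.8/6) = 0.6583.

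**Reproducing the printed figure.** The limits are 0.50 × exp(±k × 0.6583).

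| Multiplier k | Nominal level | Limits |
|---|---|---|
| 1 | 68.3% | 0.259-0.966 |
| 1.2816 | 80% | 0.215-1.162 |

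The first row rounds to the printed 0.26-0.97 at both ends. Working back from the printed limits, k = ln(0.97/0.26)/(2 × 0.6583) = 1.000. Allowing for rounding, the lower limit permits k from 0.964 to 1.023 and the upper limit 0.999 to 1.015. Together they leave 0.999 to 1.015, a nominal level of 68.2% to 69.0%.

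**Other two-sample 80% methods with 30 per arm.** Score 0.22-1.13; profile likelihood 0.20-1.12; log-adjusted 0.25-1.18; one-sided 80% multiplier (0.8416) 0.29-0.87. None gives the printed limits. The log method at a true 80% would need 48 or 49 per arm to print 0.26-0.97 (0.257-0.974 at 48, 0.258-0.967 at 49), and no section plans that number.

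**Control rate treated as known.** The parenthesis in the quoted sentence could mean that 0.20 is fixed, so that only the XFBD proportion (3/30) varies. The 80% limits for that proportion, divided by 0.20, are:

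| Method | Limits |
|---|---|
| Log | 0.248-1.009 |
| Wilson | 0.247-0.961 |
| Complementary log-log | 0.245-0.991 |
| Logit | 0.242-0.975 |
| Jeffreys | 0.241-0.944 |
| Agresti-Coull | 0.233-0.975 |
| Clopper-Pearson | 0.187-1.046 |
| Wald | 0.149-0.851 |

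None of these eight has a lower limit that rounds to 0.26. Six exclude 1 and two include it.

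**Size of the discrepancy (two-sample reading).** The ratio of upper to lower limit is 0.97/0.26 = 3.73 as printed and exp(2 × 1.2816 × 0.6583) = 5.40 at 80%. The log-scale width as printed is 1/1.2816 = 78% of the correct width. Enumerating both binomials at true rates 0.10 and 0.20 with 30 per arm (0.5 added when a cell is zero), exact coverage is 68.4% for k = 1 and 83.5% for k = 1.2816.

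**Check points for Figure 2 at 6/30.** At a true 80% the interval is 0.106-0.294 (Wald) or 0.123-0.308 (Wilson). With a multiplier of 1 it would be 0.127-0.273 (Wald) or 0.137-0.282 (Wilson).

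**The case against.** The best defence is the fixed-control reading. Under it, Wilson (0.247-0.961) and logit (0.242-0.975) fall within 0.01 to 0.02 of the printed limits and also exclude 1. The error would then be trivial, and the 68% coverage figure would not apply. The list of eight methods is also not exhaustive. With the control rate fixed, a uniform-prior credible interval is 0.287-1.015, and a Beta(2/3, 2/3) prior gives 0.256-0.968, which does round to 0.26-0.97. Figure 1 might name the method.

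Part of this stands. The multiplier of 1 remains an inference, and the coverage and width statements hold only on the two-sample reading. But that reading fits the text better: the sentence supposes that both estimated rates are attained in the pilot, and the interval is attached to their ratio. A multiplier of 1 reproduces both limits with no further assumption. The one fixed-control match found needs an unusual prior, and nothing in the plan suggests that it was used.

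A second defence is that little depends on the number. Section 10.4 itself advises against sizing a later trial from the pilot effect and says that the most recent data will be used. Section 10.6 states, "This pilot study is not powered to find statistically significant differences by treatment group", and section 10.6.1 restricts the health-event analyses to use "for future planning purposes only". This is right, and it limits the consequence. The wider interval in fact strengthens the section's own argument about instability. The label and the limits still disagree.

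**Conclusion.** The concern holds. For 3/30 v 6/30 the two-sample 80% interval is 0.22-1.16 (log) or 0.22-1.13 (score), and it includes 1. The printed 0.26-0.97 is numerically a one-standard-error interval with about 68% coverage. This rests on 30 analysed per arm and on both arms contributing sampling error. If the control rate was meant to be fixed, the standard methods tried still do not give the printed limits, but the gap can be small and whether 1 is included depends on the method.

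The effect is confined to this statement and, possibly, to the two figures. The 30 per arm was not derived from the interval, and no planned analysis uses it. It should be corrected because it is the only precision figure for the treatment effect in the readable sample-size text, and it overstates the precision.

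**What to change.** In section 10.4, replace the limits with 0.22-1.16 and state the method (log relative risk, 30 per arm), or keep the limits and relabel the interval as 68%. Add one sentence saying that the two-sample 80% interval would include 1 even if the assumed rates were observed. If a fixed control rate was intended, say so, name the method and print its limits.

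Check the multiplier behind Figures 1 and 2, using the values at 6/30 given above for Figure 2, and redraw only if it is wrong.

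The cost is one number or label, one sentence, and a check of two figures. The stated precision becomes less favourable; the sample size, design and analyses do not change.
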